1. INTRODUCTION

Dietary fibres have long been recognized for their important role in a healthy diet due to their negative association with, and even management of, chronic diseases such as obesity, diabetes, metabolic syndrome, cardiovascular disease and inflammatory-bowel disease among others (1–3). Emerging evidence has suggested that these benefits could largely be attributed to short chain fatty acids (SCFA) (acetate, propionate and butyrate), the main by-products of fibre fermentation in the gut (1,4). Our research group has demonstrated that a long-term elevation in the SCFA propionate significantly reduced body weight gain in overweight adults and reduced liver fat storage (5).

The current project will examine potential mechanisms for the positive effect of propionate on energy homeostasis and metabolic profile. We will examine the effects of propionate on circulating glucose, insulin and lipid levels at rest, following moderate-intensity exercise and mixed meal tolerance test.

To acutely increase propionate absorption from the gut the present project will use a simple nutritional supplement: sodium propionate in a hydroxypropylmethyl cellulose (HPMC) capsule. This capsule is coated with an enteric film which prevents gastric digestion until the capsule reaches the intestine. This nutritional supplement has been used in human volunteers in a previously approved ethics application (12/LO/1769: Oral propionate and glucose homeostasis). A 5g acute dose of sodium propionate had previously been tested and reported no adverse effects (6) . The MHRA have confirmed that encapsulated sodium propionate is not classed as an investigative medicinal product (correspondence attached with application).

STUDY: The acute effects of short chain fatty acids on energy homeostasis

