An intervention which elevates propionate release from the gut may therefore protect against obesity and its associated metabolic disruptions through enhanced glucose tolerance, lipid profile, and increased energy expenditure. Thus, the aim of this project is to investigate the acute effects of gut-derived propionate on the regulation of energy expenditure, substrate oxidation and overall metabolic profile in humans throughout different physiological states (fasting, postprandial and during physical activity). This study is an extrapolation based on a previously ethically approved research study (15/WA/0415) which demonstrated an increase in energy expenditure, lipid oxidation rates and circulating levels of propionate following an acute dose of 5 g sodium propionate supplemented over a 180 min time period. As can be seen from the below graphs, circulating levels of propionate increased over time to reach a peak at 180 min and thus for this study we would want to determine the trend in propionate levels over a longer period (300 minutes) while also examining energy expenditure and lipid oxidation with a properly matched energy control.

[figure not shown]

Figure 1. The effect of oral propionate supplementation on short chain fatty acid levels in peripheral blood. A. Propionate (Time×Trial: $P= 0.043$) and B. propionate iAUC ($P=0.021$).

[figure not shown]

Figure 2. The effect of oral propionate supplementation on resting energy expenditure and substrate oxidation. A. Resting energy expenditure (TimexTrial: $P= 0.388$) and **B.** resting energy expenditure iAUC ($P=0.036$). **C.** Lipid oxidation (TimexTrial: $P= 0.075$) and **D.** lipid oxidation iAUC ($P=0.019$).

2. Study 1: The acute effects of propionate on energy metabolism during fasting.

Study methodology: A randomized, placebo controlled, double blind, cross-over study.

Participants: 40 healthy male and female volunteers aged between 18 and 65 years with body mass index (BMI) of 18-35 kg/m².

Support of number of volunteers: A power calculation confirmed that 34 participants would be sufficient to detect a 5% difference in the primary outcome, resting energy expenditure, with a standard deviation (SD) of 10 %($\alpha=0.05$, power=0.80). 40 participants were recruited to allow a dropout rate of 15%.

Recruitment

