Volunteers will be recruited via email using a healthy volunteer database of the NIHR/Wellcome Trust Imperial Clinical Research Facility (CRF) or via a study advertisement. Interested volunteers will be asked to fill in a pre-screening questionnaire and if deemed eligible will be invited for a screening visit at the CRF in Hammersmith Hospital.

Visit 1- Health Screening

Participants will attend the NIHR/Wellcome Trust Imperial Clinical Research Facility at Hammersmith Hospital where their eligibility will be assessed via an interview which discusses medical history, family history of medical illness and drug history. They will have a blood test (Full blood count liver function test, urea & electrolytes and lipids) and height and weight measurements will also be taken. They will also have an electrocardiogram (ECG) and blood pressure will be recorded. All women of child bearing age will have a pregnancy test. These results will be examined and approved by a qualified research doctor before the volunteers will be formally enrolled in the study.

Visits 2,3,4– Study Visits

Subjects will be asked to complete three study visits that will last approximately 6 hours each. The three study visits will need to be separated by a period of at least 3 days. Participants will be told not to start any other new diets or intensive exercise regimes during the study period as this may give us conflicting results.

In a randomized order, volunteers will complete the following three study visits:

1. Sodium Chloride (Sodium Control)
2. Palmitic Acid (Fatty Acid Control)
3. Sodium Propionate

[figure not shown]
The day prior to each study visit, participants will be requested to refrain from strenuous exercise, caffeine and alcohol. Participants will then be requested to fast overnight (they are allowed to drink water) and will come to the NIHR/Wellcome Trust Imperial Clinical Research Facility at Hammersmith Hospital the following morning. Fasting blood samples will be taken through an intravenous peripheral cannula at -15 and 0 min.

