Between the fasting blood samples, resting energy expenditure will be measured with a standard indirect calorimeter. The calorimeter captures expired air from a large, transparent canopy, worn over the head and thorax, and is typically very well tolerated. Each participant will be asked to lie in a semi-recumbent position under the canopy. Measurements will be taken for 20 min in order to assess the participants' resting metabolic rate (RMR) and respiratory quotient (RQ). Additional measures of RMR and RQ will be recorded at 40-60 min, 100-120 min, 160-180, 220-240 min and 280-300.

Following the 0 min sample volunteers will ingest a capsule containing either 1g sodium propionate (Propionate) or 1 g sodium chloride (Sodium Control) or 1g palmitic acid (fatty acid control) at 30, 60, 90 and 120 (5g in total)

Blood samples will be taken at 30, 60, 90, 120, 150, 180, 210, 240 and 300 min to measure hormones and metabolites. 110 ml (11 × 10 ml) will be collected throughout each study visit. Blood pressure and heart rate will be measured at baseline and every hour at 60, 120, 180, 240 and 300 min. Urine will be collected throughout the study visit to measure urea concentrations for calculation of protein oxidation rates. Subjects will empty their bladder before baseline blood samples and collect all urine thereafter for a period of 300 min using appropriate measurement containers.

Figure 1: Study visit protocol for study 1.

3. Study 2: The acute effects of propionate on energy metabolism during exercise.

Study methodology: A randomized, placebo controlled, double blind, cross-over study.

Participants: 40 healthy male and female volunteers aged between 18 and 65 years with body mass index (BMI) of 18-35 kg/m².

Support of number of volunteers: A power calculation confirmed that 34 participants would be sufficient to detect a 5% difference in the primary outcome, resting energy expenditure, with a standard deviation (SD) of 10 % ($\alpha=0.05$, power=0.80). 40 participants were recruited to allow a dropout rate of 15%.

Recruitment

Volunteers will be recruited via email using a healthy volunteer database of the NIHR/Wellcome Trust Imperial Clinical Research Facility (CRF) or via a study advertisement. Interested volunteers will be asked to fill in a pre-screening questionnaire and if deemed eligible will be invited for a screening visit at the CRF in Hammersmith Hospital.

Visit 1- Health Screening

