6. REGULATORY ISSUES

ETHICS APPROVAL

This study is awaiting ethical approval from the Wales REC 6 Ethics Committee. The study will be conducted in accordance with the recommendations for physicians involved in research on human subjects adopted by the 18th World Medical Assembly, Helsinki 1964 and later revisions. Amendments to the protocol should be approved by the sponsor before being sent to ethics.

CONSENT

Consent to enter the study must be sought from each participant only after a full explanation has been given, an information leaflet offered, and time allowed for consideration. Signed participant consent should be obtained. The right of the participant to refuse to participate without giving reasons must be respected. After the participant has entered the study the clinician remains free to

give alternative treatment to that specified in the protocol at any stage if he/she feels it is in the participant's best interest, but the reasons for doing so should be recorded. In such cases, the participants remain within the study for the purposes of follow-up and data analyses. All participants are free to withdraw at any time from the study without giving reasons and without prejudicing further treatment.

CONFIDENTIALITY

The Chief Investigator will preserve the confidentiality of participants in the study and is registered under the Data Protection Act.

DATA AND SAMPLE COLLECTION AND ANALYSIS

All data and samples will be collected at the NIHR/Wellcome Trust Imperial Clinical Research Facility at Hammersmith Hospital. All data and samples will be stored and analysed at the laboratories of the Department of Investigative Medicine, Hammersmith Hospital. They data and samples will be available only to the study researchers. All analysis will be carried out on anonymised samples. The code linking samples to the donor will only be broken once all analysis has been conducted.

INDEMNITY

Imperial College holds negligent harm and non-negligent harm insurance policies, which apply to this study.

SPONSOR

Imperial College London will act as the main sponsor for this study. Delegated responsibilities will be assigned to the NHS trusts taking part in this study.

REIMBURSMENT

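### The sodium chloride arm named as the sodium control is matched by weight, so it gives about 64% more sodium than sodium propionate, and no pair of arms holds sodium constant

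*Combined protocol and SAP*

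**What the plan says.** The study-visit text of Section 2 (Study 1), Section 3 (Study 2) and Section 4 (Study 3) uses the same dosing sentence. Each capsule contains "1g sodium propionate (Propionate) or 1 g sodium chloride (Sodium Control) or 1g palmitic acid (fatty acid control"). A capsule follows the 0 min sample, with further capsules "at 30, 60, 90 and 120 (5g in total"). The list of conditions in each study repeats the label "Sodium Chloride (Sodium Control").

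The text gives no sodium content for any arm, no molar equivalence, and no mention of sodium added to the palmitic acid capsules. The only matching it mentions is in the Introduction, which speaks of "examining energy expenditure and lipid oxidation with a properly matched energy control". Each study is described as "A randomized, placebo controlled, double blind, cross-over study", without saying which arm is the placebo. The primary outcome in all three studies is resting energy expenditure. Blood pressure and heart rate are measured at baseline and hourly.

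**The concern.** Giving propionate as its sodium salt also gives sodium. A sodium control is there to separate the two: if it delivers the same sodium without the propionate, the difference between the arms is not due to sodium. That requires equal moles of sodium. Equal weights cannot provide this, because each salt carries one sodium per formula unit and the formula weights differ.

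At stake is how the propionate-minus-sodium-chloride difference is interpreted, for resting energy expenditure and for anything else measured. If sodium differs between the arms, that difference mixes the effect of propionate with the effect of a lower sodium load. The comparison with palmitic acid does not help, because there propionate is the arm with more sodium.

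**Working it through.** **Inputs from the protocol.** 1 g of compound per capsule in every arm, and 5 g in total per visit (Sections 2, 3 and 4, study-visit text).

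**Inputs not in the protocol.** Formula weights, which are chemical constants: sodium chloride 58.44, anhydrous sodium propionate 96.06, sodium 22.99, water 18.015 g/mol. Palmitic acid contains no sodium. The protocol gives neither purity nor hydration, so pure anhydrous salts are assumed first and then varied, with any impurity taken as sodium-free.

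**The plan's own dose figure.** One capsule at 0 min plus four more is 5 × 1 g = 5 g, as stated.

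**Sodium per arm.** mmol = 1000 × grams / formula weight.

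- Per 1 g: sodium chloride 1000/58.44 = 17.11 mmol; sodium propionate 1000/96.06 = 10.41 mmol; palmitic acid 0.
- Per 5 g: 85.56, 52.05 and 0 mmol.
- As grams of sodium: 85.56 × 22.99 / 1000 = 1.97 g; 52.05 × 22.99 / 1000 = 1.20 g; 0 g.
- Ratio of sodium chloride to propionate: 96.06/58.44 = 1.644, that is 64% more.

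**Contrasts in sodium per visit.**

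- Propionate minus sodium chloride: 52.05 − 85.56 = −33.5 mmol (−0.77 g).
- Propionate minus palmitic acid: +52.1 mmol.
- Sodium chloride minus palmitic acid: +85.6 mmol.

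None is zero.

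**Sensitivity to salt form (per 5 g).**

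| Assumption | Sodium chloride, mmol | Propionate, mmol | Excess, mmol | Ratio |
|---|---|---|---|---|
| Pure anhydrous salts | 85.56 | 52.05 | 33.5 | 1.64 |
| Sodium chloride 95% pure | 81.28 | 52.05 | 29.2 | 1.56 |
| Propionate 95% pure | 85.56 | 49.45 | 36.1 | 1.73 |
| Propionate hemihydrate (105.07 g/mol) | 85.56 | 47.59 | 38.0 | 1.80 |
| Propionate monohydrate (114.08 g/mol) | 85.56 | 43.83 | 41.7 | 1.95 |

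Against pure anhydrous propionate, sodium would be equal only if the sodium chloride were 58.44/96.06 = 60.8% pure. If 1 g meant the propionate ion rather than the salt, which the text does not say, propionate would carry 1000/(96.06 − 22.99) = 13.69 mmol per capsule and the ratio would be 17.11/13.69 = 1.25.

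**Number of capsules.** If only the four later times were dosed (4 g), the figures are 68.4 and 41.6 mmol, an excess of 26.8 mmol (0.62 g) with the same ratio.

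**Sodium-matched dose.** Sodium chloride per 1 g of propionate salt = 58.44/96.06 = 0.608 g, or 3.04 g per visit. Both arms then give 52.1 mmol. For the other salt forms it is 0.640 g (sodium chloride 95% pure), 0.578 g (propionate 95% pure), 0.556 g (hemihydrate) and 0.512 g (monohydrate). Filler to restore 1 g is 1 − 0.608 = 0.392 g per capsule, or 1.96 g over five capsules.

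**The case against.** The strongest reply is that the protocol never promises equal sodium. The label is two words, and a sodium salt without propionate is a sodium control in a loose sense. The only matching stated concerns energy. Equal weight is also a reasonable choice for a double-blind capsule study, particularly if sodium chloride is the energy-free placebo. The protocol does not say that it is, but that is the natural reading. All of this stands, and it limits the point to the sodium role that the label claims.

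Second, no harm is shown. The documents do not allow the size or direction of a sodium effect on resting energy expenditure, blood pressure or heart rate to be calculated. The two controls also bracket propionate (0 < 52.1 < 85.6 mmol, and the same order holds for every salt form tried). A propionate result beyond both controls is therefore hard to explain by a monotone sodium effect. That too stands, but it does not cover a result that differs from only one control or lies between the two. The protocol does not say that propionate must differ from both.

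Third, reformulating one arm leaves the 52.1 mmol gap between propionate and palmitic acid. That is correct, but it does not remove the gain: one contrast would hold sodium constant where now none does.

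Finally, the purity and hydrate cases are hypothetical. They are there to show that the direction does not depend on salt form. They are not estimates of the material used.

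**Conclusion.** The point holds. Dosed by weight, the arm named as the sodium control gives 85.6 mmol sodium per visit against 52.1 mmol with propionate, an excess of 33.5 mmol or 64%, in all three studies. This rests on pure anhydrous salts and five capsules. Across the purities and hydrates tried the excess is 56% to 95%; reading the gram dose as propionate ion would leave 25%. In no case is sodium equal between any two arms.

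The propionate-minus-sodium-chloride contrast therefore cannot be described as sodium-controlled. No bias in any outcome is claimed, because the documents give nothing from which to compute one. It should be corrected, but it does not invalidate the design.

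**What to change.** In the dosing sentence of Sections 2, 3 and 4, replace the 1 g sodium chloride dose with about 0.61 g per capsule (about 3.04 g against 5 g sodium propionate). Set the exact amount from the certificates of the salts supplied, and state the mmol of sodium in each condition. If capsule weight must be kept, make it up with an energy-free filler that is not fermentable. The Introduction describes the acids under study as "the main by-products of fibre fermentation in the gut", so a fermentable filler could produce them in the control arm.

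The cost is one reformulated control capsule for all three studies and, if weight is made up, about 0.39 g filler per capsule (1.96 g per visit) that the propionate arm lacks. Capsule size and appearance are not given, so the blind should be rechecked. There are no extra participants, visits or samples, and the sample size of 34 evaluable and 40 recruited is unaffected.

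Whether reformulation is still possible is unclear. Section 6 says "This study is awaiting ethical approval from the Wales REC 6 Ethics Committee", while the sample-size paragraphs are in the past tense ("40 participants were recruited to allow a dropout rate of 15" per cent). If the capsules already exist, the change is to wording only: call the arm a weight-matched sodium chloride placebo, report the mmol of sodium per arm, and do not interpret its difference from propionate as sodium-controlled.

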The day prior to each study visit, participants will be requested to refrain from strenuous exercise, caffeine and alcohol. Participants will then be requested to fast overnight (they are allowed to drink water) and will come to the NIHR/Wellcome Trust Imperial Clinical Research Facility at Hammersmith Hospital the following morning. Fasting blood samples will be taken through an intravenous peripheral cannula at -15 and 0 min.

Between the fasting blood samples, resting energy expenditure will be measured with a standard indirect calorimeter. The calorimeter captures expired air from a large, transparent canopy, worn over the head and thorax, and is typically very well tolerated. Each participant will be asked to lie in a semi-recumbent position under the canopy. Measurements will be taken for 20 min in order to assess the participants' resting metabolic rate (RMR) and respiratory quotient (RQ). Additional measures of RMR and RQ will be recorded at 40-60 min, 100-120 min, 160-180 220-240 min and 280-300.

Following the 0 min sample volunteers will ingest a capsule containing either 1g sodium propionate (Propionate) or 1 g sodium chloride (Sodium Control) or 1g palmitic acid (fatty acid control) at 30, 60, 90 and 120 (5g in total)

At 180 min, volunteers will have their heart rate recorded while they complete 60 min of constant-load cycling at a workload corresponding to 40% Wmax, determined from Visit 2 whilst breathing through a mouthpiece connected to an indirect calorimeter to determine energy expenditure and substrate oxidation rates during exercise. Blood samples will be taken at 30, 60, 90, 120, 150, 180, 210, 240 and 300 min to measure hormones and metabolites. 110 ml (11 × 10 ml) will be collected throughout each study visit. Blood pressure and heart rate will be measured at baseline and every hour at 60, 120, 180, 240 and 300 min. Urine will be collected throughout the study visit to measure urea concentrations for calculation of protein oxidation rates. Subjects will empty their bladder before baseline blood samples and collect all urine thereafter for a period of 300 min using appropriate measurement containers.

Figure 2: Study visit protocol for study 2.

4. Study 3: The acute effects of propionate on postprandial metabolism:

Study methodology: A randomized, placebo controlled, double blind, cross-over study.

Participants: 40 healthy male and female volunteers aged between 18 and 65 years with body mass index (BMI) of 18-35 kg/m².

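### Studies 2 (exercise) and 3 (postprandial) carry over Study 1's primary outcome, so no exercise measure or post-meal window is primary, and one Study 2 resting window falls inside the ride

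*Combined protocol and SAP*

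**What the plan says.** The Introduction gives two statements of purpose. One concerns "circulating glucose, insulin and lipid levels at rest, following moderate-intensity exercise and mixed meal tolerance test". The other concerns energy expenditure, substrate oxidation and metabolic profile "throughout different physiological states (fasting, postprandial and during physical activity").

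Section 3 (Study 2) is titled "The acute effects of propionate on energy metabolism during exercise", and section 4 (Study 3) is about postprandial metabolism. The sample-size paragraphs of sections 2, 3 and 4 are nevertheless the same. Each says that 34 participants are "sufficient to detect a 5% difference in the primary outcome, resting energy expenditure", with SD 10%, alpha 0.05 and power 0.80, and that 40 are recruited for 15% dropout.

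The Study 2 visit description contains three relevant statements:

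- For the resting measure: "Each participant will be asked to lie in a semi-recumbent position under the canopy". The later resting measures are then scheduled: "Additional measures of RMR and RQ will be recorded at 40-60 min, 100-120 min, 160-180 220-240 min and 280-300".
- For the ride: "At 180 min, volunteers will have their heart rate recorded while they complete 60 min of constant-load cycling".
- For gas exchange while cycling: participants are "breathing through a mouthpiece connected to an indirect calorimeter to determine energy expenditure and substrate oxidation rates during exercise".

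Study 3 lists the same five calorimetry windows, gives a 500 kcal drink at 180 min, and takes blood at 195, 210, 240 and 300 min after it.

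Nowhere does the combined document say which window, or which summary of the windows (single value, mean, incremental area, change from baseline), is the primary measure.

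**The concern.** Until 180 min the three studies follow essentially the same fasting, resting schedule; Study 3's baseline calorimetry is 15 rather than 20 min. The ride and the drink are what make Studies 2 and 3 different from Study 1, yet neither is tied to a primary outcome. Two consequences follow.

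- **The primary can miss the study's own question.** If it is taken from windows up to 180 min, Studies 2 and 3 repeat Study 1. If it is taken from later windows, it concerns a different physiological state. The text allows either choice, and nothing fixes it before the data are seen.
- **In Study 2 a value taken during cycling can carry the primary outcome's name.** An analyst who averages every listed resting window would include a measurement made on the ergometer.

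The choice of summary can also matter. For the earlier 180 min study, the Introduction's legend for resting energy expenditure reports P=0.388 for the time-by-trial interaction and P=0.036 for the incremental area. These test different hypotheses, so the plan should say which one is meant.

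**Working it through.** **1. The plan's own figure.** Inputs from the sample-size paragraphs: difference 5%, SD 10%, alpha 0.05, power 0.80, dropout 15%. Assumptions not stated in the document: a two-sided test of one paired contrast, with 10% as the SD of the within-person differences.

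- Standardised difference d = 5/10 = 0.5.
- Power from the noncentral t distribution with n - 1 degrees of freedom and noncentrality d × √n. At n = 34, noncentrality is 0.5 × √34 = 2.92 and the critical t is 2.035.
- Power is 0.795 at n = 33 and 0.808 at n = 34, so 34 is the smallest sufficient number.
- Recruitment: 34 / (1 - 0.15) = 40.

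Both figures reproduce. They are figures for resting energy expenditure.

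**2. Windows against events.** The ride starts at 180 min and lasts 60 min, so it occupies 180-240 min. The overlap of a window (a, b) with it is max(0, min(b, 240) - max(a, 180)).

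| Window (min) | Overlap with ride (min) | State, Study 2 | State, Study 3 |
|---|---|---|---|
| 40-60 | 0 | before ride | before meal |
| 100-120 | 0 | before ride | before meal |
| 160-180 | 0 | before ride | before meal |
| 220-240 | 20 of 20 | in ride | after meal |
| 280-300 | 0 | starts 40 min after ride | after meal |

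Of 100 scheduled minutes, Study 2 has 60 before, 20 during and 20 after the ride. Study 3 has 60 before and 40 after the meal. A participant cannot be both cycling and semi-recumbent under a canopy at 220-240 min.

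**3. What 34 completers could detect on another primary.** The document gives no effect or SD for ride energy expenditure, post-meal energy expenditure, glucose or insulin, so power for these cannot be derived from it. Two things can be stated.

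- Smallest difference with 80% power at n = 34: 0.495 SD of the paired differences for one contrast at two-sided 0.05. If both controls were tested at 0.025 each (an assumption, since no primary contrast is named), it is 0.55 SD.
- Power for a 5% effect at n = 34 over a range of assumed paired SDs, two-sided 0.05:

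| Assumed paired SD | d | Power |
|---|---|---|
| 10% | 0.500 | 0.81 |
| 12% | 0.417 | 0.65 |
| 15% | 0.333 | 0.47 |
| 20% | 0.250 | 0.29 |

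**The case against.** The best defence is that a common primary is the sponsor's to choose. Resting energy expenditure is the outcome with earlier support in the Introduction, which also gives a reason to follow participants to 300 min. The sample size reproduces, and each power sentence already names resting energy expenditure, so no power is claimed for exercise, glucose or insulin. All of this stands. It means that the plan must either change the primary or say openly that the exercise and post-meal results are secondary. At present it does neither.

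The 220-240 min entry may well be only a labelling slip, since the same section describes mouthpiece calorimetry during the ride. That is the likeliest explanation, and the missing visit figure may confirm it. The text still needs reconciling, because the label is that of the primary outcome.

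A reader might infer more than the document supports:

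- *That exercise goes untested.* It does not. Energy expenditure and substrate oxidation are measured during the ride; they are simply not primary.
- *That the treatment comparison is biased.* It is not. Each participant has the same ride or drink at every visit.
- *That Study 3's schedule is unworkable.* Its 220-240 and 280-300 min windows are feasible and can carry a postprandial outcome. They are just not designated.
- *That calling 280-300 min resting in Study 2 is an error.* It begins 40 min after the ride and could be a semi-recumbent measure. The plan need only say whether it counts as rest or recovery.
- *That the Introduction contradicts itself on exercise.* One statement concerns blood levels after exercise, the other energy expenditure, oxidation and metabolic profile during it. The schedule can serve both.
- *That Study 1 is free of the gap.* It is not. Its windows share a fasting, resting state but differ in how much has been ingested: 40-60 min precedes the capsules listed at 60, 90 and 120 min, while 160-180 min follows them all.

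**Conclusion.** The point holds and should be fixed. Studies 2 and 3 inherit a primary outcome that does not designate the state each was set up to examine, and none of the three studies defines its primary window or summary. The Study 2 schedule also contradicts itself for one of five post-baseline windows, with complete overlap.

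The sample-size arithmetic is sound for resting energy expenditure, provided that 10% is the SD of paired differences, the test is two-sided and there is one contrast. It cannot be carried over to an exercise or post-meal outcome. The powers at SDs of 12%, 15% and 20% illustrate assumed values and are not estimates for this trial. The reading of 220-240 min as mislabelled in-ride calorimetry is probable rather than established.

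**What to change.** 1. **Reconcile the Study 2 schedule.** Bring the 220-240 min entry into line with the ride, and keep any in-ride value out of the resting energy expenditure summary. State whether 280-300 min is rest or recovery.
2. **Name one primary outcome, window and summary in each study, from data already scheduled.** For Study 2, use a measure from the ride calorimetry, for example mean energy expenditure over 180-240 min. For Study 3, use a post-meal measure, for example mean energy expenditure over 220-240 and 280-300 min. Adjust each for that visit's pre-dose baseline, and keep resting energy expenditure before 180 min as secondary. Study 1 needs its window and summary named too. If the sponsor prefers to keep resting energy expenditure as primary throughout, say so, and state that the exercise and post-meal results are secondary and not covered by the stated power.
3. **Do not carry the 80% figure over to a new primary.** Give the assumed effect and within-person SD, or the difference detectable with 34 completers as in the working, and state how many contrasts are tested and at what alpha.

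Cost: changes to the text only, with no extra participants, visits or measurements proposed. The price is that stated power for Studies 2 and 3 may become less favourable, and the three studies would no longer share one primary outcome.
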